 - ANC $\geq 1500/\mu\text{L}$ assessed at least 2 weeks after growth factor support, if applicable
 - platelet count $\geq 100 \times 10^9/\text{L}$ assessed at least 2 weeks after transfusion with blood products, if applicable
 - hemoglobin ($\geq 8.0 \text{ g/dL}$) assessed at least 2 weeks after transfusion with blood products and/or growth factor support, if applicable
 - serum bilirubin $\leq 1.5 \times$ upper limit of normal (ULN) or direct bilirubin $\leq 3 \times$ ULN in subjects diagnosed with Gilbert’s syndrome
 - estimated glomerular filtration rate (GFR) $\geq 30 \text{ mL/min}/1.73 \text{ m}^2$ using the Modification of Diet in Renal Disease (MDRD) study equation as applicable (see Section [7.6.3](#))
 - alanine aminotransferase (ALT) and aspartate aminotransferase (AST) $\leq 1.5 \times$ ULN (if liver metastases are present, then $\leq 3 \times$ ULN is allowed)

5. Subjects of childbearing potential as defined in Section 4.3, under the following conditions:
 - Must have a negative serum or urine pregnancy test (minimum sensitivity 25 mIU/mL or equivalent units of beta human chorionic gonadotropin [β -hCG]) result within 3 days prior to the first dose of LV. Subjects with false positive results and documented verification that the subject is not pregnant are eligible for participation.
 - Must agree not to try to become pregnant during the study and for at least 6 months after the final dose of study drug administration
 - Must agree not to breastfeed or donate ova, starting at time of informed consent and continuing through 6 months after the final dose of study drug administration
 - If sexually active in a way that could lead to pregnancy, must consistently use 2 highly effective methods of birth control (as defined in [Appendix K](#)) starting at time of informed consent and continuing throughout the study and for at least 6 months after the final dose of study drug administration
6. Subjects who can father children, under the following conditions:
 - Must agree not to donate sperm starting at time of informed consent and continuing throughout the study period and for at least 6 months after the final study drug administration

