5.2.3.1. Dosing Criteria

The following laboratory criteria must be met on Day 1 of each cycle prior to LV administration:

- Neutrophil count $\geq 1000/\mu\text{L}$ (\leq Grade 2)
- Aspartate aminotransferase \leq Grade 2
- ALT \leq Grade 2
- Total bilirubin \leq Grade 2

In Part B and C, neutrophil count must be $\geq 1000/\mu\text{L}$ (\leq Grade 2) prior to LV administration on Day 8 and Day 15 (if receiving q1wk dosing) of each cycle.

If the above criteria are not met on the day of dosing, hold the LV dose until the criteria are met. In addition, hold LV dosing for subjects with \geq Grade 2 peripheral neuropathy (see Table 10).

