5.2.4. Dose Modifications

5.2.4.1. Part A (q3wk dosing)

Dose modification guidelines for LV q3wk treatment-associated toxicity are described in [Table 9](#). The maximum doses after modifications are:

- 200 mg for subjects reduced to 2.0 mg/kg
- 150 mg for subjects reduced to 1.5 mg/kg

Table 9: Q3wk LV dose levels

Dose Level	Dose	Maximum Dose
Starting dose	2.5 mg/kg	250 mg
-1	2.0 mg/kg	200 mg
-2	1.5 mg/kg	150 mg

[Table 10](#) describes dose modifications for LV treatment-associated toxicity.

Doses reduced for LV-related toxicity should not be re-escalated.

If a subject has a clinically significant, unresolved AE on Day 1 of C2 or beyond, the start of the cycle may be delayed for up to 14 days. Delays of >14 days must be approved by the medical monitor.

In the event a subject is unable to tolerate their dose level, additional treatment cycles (C2 or later) may be administered at a lower dose level upon approval by the medical monitor.

Table 10: Dose modifications for LV-associated toxicity (Part A; q3wk dosing)

Toxicity	Grade 1	Grade 2	Grade 3	Grade 4
Peripheral neuropathy ^a	Continue at same dose level	Withhold until toxicity resolves to \leq Grade 1; then resume treatment at the next lower dose level	Withhold until toxicity resolves to \leq Grade 1, then resume treatment at the next lower dose level	Discontinue treatment
Non-hematologic ^a (except peripheral neuropathy and hyperglycemia)	Continue at same dose level	Continue at same dose level	Withhold dose until toxicity is \leq Grade 2 or has returned to baseline, then resume treatment at same dose level ^b	Withhold dose until toxicity is \leq Grade 2 or has returned to baseline, then reduce dose to the next lower dose level and resume treatment, or discontinue at the discretion of the investigator ^{b,c}
Hematologic ^a	Continue at same dose level	Continue at same dose level	Withhold until toxicity resolves to \leq Grade 2 or baseline ^{d,e} . For neutropenia, strongly consider G-CSF support , then resume treatment at the same dose level. Prophylactic G-CSF support should be strongly considered for subsequent cycles. (See Appendix G)	Withhold until toxicity resolves to \leq Grade 2 or baseline ^{d,e} . For neutropenia, strongly consider G-CSF support , then resume treatment at the same dose level. Prophylactic G-CSF support is required for all subsequent cycles. If Grade 4 neutropenia recurs despite G-CSF support, consider dose reduction to dose level -1 or discontinuation. (Appendix G)

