5.2.4.2. Part B (q1wk dosing) and Part C (Arm 3; q1wk dosing)

In the event of an AE or lab criteria that prevents dosing of LV (see Section 5.2.3.1), the LV dose for the week should be withheld. LV may be resumed when the dosing criteria are met. If a dose(s) of LV is withheld, the corresponding visit may be skipped and resume the following week (eg, if the Day 8 dose is skipped, visits will resume on Day 15; if Day 8 and Day 15 doses are skipped, visits will resume on Day 1 of the following cycle). Day 1 of a cycle may be delayed but not skipped.

Dose reduction of LV may be considered in the event of recurrent AE despite withheld doses. Dose re-escalation following dose reduction is not allowed. Dose levels for LV dose reductions in Part B and Part C (Arm 3) are shown in [Table 11](#).

For Part C (Arm 3), subjects who discontinue pembrolizumab due to a pembrolizumab-related AE (see Section 5.3.4) may continue LV. Similarly, subjects who discontinue LV for a LV-related AE may continue pembrolizumab. See Section 5.5.3 for details on managing overlapping AEs.

Table 11: Q1wk LV dose reductions

Starting Dose	First Dose Reduction (mg/kg/wk)	Second Dose Reduction (mg/kg/wk)
Starting dose 1.0 mg/kg/wk	0.75	0.5
Starting dose 1.25 mg/kg/wk	1.0	0.75

For nonclinical events requiring alteration in dosing schedule (eg, holidays, scheduling conflicts), a +2 day dosing window is allowed. Nonclinical events that require skipping a dose(s), must be approved by sponsor medical monitor. At least 7 days must elapse between each administration of LV.

Dose modification guidelines for LV q1wk treatment-associated toxicity are detailed in [Table 12](#).

Table 12: Dose modifications for LV treatment-associated toxicity (Part B and Part C [Arm 3] q1wk dosing)

Toxicity	Grade 1	Grade 2	Grade 3	Grade 4
Peripheral neuropathy ^a	Continue at same dose level	Withhold until toxicity resolves to \leq Grade 1; treatment may resume at the next lower dose level (see Table 11)	Withhold until toxicity resolves to \leq Grade 1, then resume treatment at the next lower dose level (see Table 11)	Discontinue treatment
Hyperglycemia		Hold for blood glucose >250 mg/dL or >13.9 mmol/L. Resume treatment once elevated blood glucose has improved to ≤ 250 mg/dL or ≤ 13.9 mmol/L and subject is clinically and metabolically stable (see Section 5.6 for details).		

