Non-hematologic ^a (except peripheral neuropathy and hyperglycemia)	Continue at same dose level	Continue at same dose level	Withhold dose until toxicity is \leq Grade 2 or has returned to baseline, then resume treatment at same dose level ^b	Withhold dose until toxicity is \leq Grade 2 or has returned to baseline, then reduce dose to the next lower dose level (see Table 11) and resume treatment, or discontinue at the discretion of the investigator ^{b,c}
Hematologic ^a	Continue at same dose level	Continue at same dose level	Withhold until toxicity resolves to \leq Grade 2 or baseline ^{d,e} , then resume treatment at the same dose level. If the dose is held >48 hours, the dose may be omitted and dosing may resume on the next scheduled dosing day. See Sections 5.4.2 and 5.4.3 on allowed concomitant therapy and myeloid growth factors.	Withhold until toxicity resolves to \leq Grade 2 or baseline ^{d,e} , then reduce dose to the next lower dose level (see Table 11) if treatment is resumed ^{b,c} . If the dose is held >48 hours, the dose may be omitted and dosing may resume on the next scheduled dosing day. If Grade 4 neutropenia recurs, reduce dose to the next lower dose level (see Table 11) if treatment is resumed, or discontinue at the discretion of the investigator. See Sections 5.4.2 and 5.4.3 on allowed concomitant therapy and myeloid growth factors.
Febrile neutropenia ^a	Not applicable	Not applicable	Withhold until febrile neutropenia resolves and neutrophil count returns to \leq Grade 2 or baseline and then resume treatment at the next lower dose level (see Table 11). If the dose is held >48 hours, the dose may be omitted and dosing may resume on the next scheduled dosing day. If febrile neutropenia recurs, reduce dose to the next lower dose level (see Table 11) if treatment is resumed, or discontinue at the discretion of the investigator. See Sections 5.4.2 and 5.4.3 on allowed concomitant therapy and myeloid growth factors.	

The maximum dose will be 200 mg per infusion for subjects enrolled in Part B and Part C (Arm 3).

- a Only 2 dose reductions are allowed without prior medical monitor approval. Additional toxicities should be managed with dose delays. Medical monitor approval is needed for further dose reduction.
- b Subjects who develop Grade 3 or 4 electrolyte laboratory abnormalities may continue study treatment without interruption if a management plan consistent with institutional practice and regular monitoring are put in place.

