5.2.4.3. Part C (Arm 1 and Arm 2; 2q3wk dosing)

In the event of an AE or lab criterion that prevents dosing of LV (see Section 7.6.1), the LV dose should be withheld until the dosing criteria are met. If the Day 1 dose is held, the Day 8 dose should not be given until 7 days later.

In the event of an AE or lab criterion that prevents dosing of LV on Day 8 during the cycle (see Section 7.6.1), the LV dose for the week may be withheld up to 4 days for Arm 1 and Arm 2. LV may be resumed when the dosing criteria are met. If a dose of LV is withheld for more than 4 days, the corresponding visit may be skipped and dosing resumed at the following visit (eg, if the Day 8 dose is skipped, visits will resume on Day 1 of the following cycle). Day 1 of a cycle may be delayed but not skipped.

Dose reduction of LV may be considered in the event of recurrent AE despite withheld doses. Dose re-escalation following dose reduction is not allowed. Dose levels for LV dose reductions in Part C (Arms 1 and 2) are shown in [Table 13](#) .

For Arm 2, subjects who discontinue pembrolizumab due to a pembrolizumab-related AE (see Section 5.3.4) may continue LV. Similarly, subjects who discontinue LV for a LV-related AE may continue pembrolizumab. See Section 5.5.3 for details on managing overlapping AEs.

Dose modification guidelines for LV 2q3wk treatment-associated toxicity are described in [Table 13](#) (Arm 1 and Arm 2).

Table 13: 2q3wk LV dose levels

Starting dose	First dose reduction	Second dose reduction ^a
1.5 mg/kg	1.25 mg/kg	1.0 mg/kg ^b

^a If patients have more than 2 dose reductions (with medical monitor approval), dose will be the next appropriate reduced dose level determined by discussion between investigator and medical monitor.

^b The dose may be reduced to 0.75 mg/kg following approval from the medical monitor.

For nonclinical events requiring alteration in dosing schedule (eg, holidays, scheduling conflicts), a +4-day dosing window is allowed. If more than a +4-day window is needed, the medical monitor must be consulted. The medical monitor must approve skipped dose(s) for nonclinical events. At least 7 days must elapse between administrations of LV.

[Table 14](#) describes dose modifications for LV treatment-associated toxicity for the 2q3wk schedule (Arm 1 and Arm 2).

Doses reduced for LV-related toxicity should not be re-escalated.

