6.3.3.3. Day 8 (± 2 days)

Predose

- Confirm subject meets dosing criteria (Section 5.2.3.1)
- Physical exam (Section 7.6.4) (C1 only)
- CBC with differential (see Section 7.6.3; results to be submitted to iRIS), Cycles 1 and 2 only
- Serum chemistry panel and liver function tests (see Section 7.6.3; results to be submitted to iRIS), Cycles 1 and 2 only
- Random blood glucose in Cycles 1 and 2. Following C2, random blood glucose may be collected as indicated in subjects at risk for hyperglycemia. (see Section 5.6; results to be submitted to iRIS)
- Vital signs (within 60 minutes prior to the start of LV infusion, see Section 7.6.2)
- Blood samples for PK assessment (C1 and C4 only; see Section 7.3 for time points)
- LV administration (a +2 day dosing window is allowed for subsequent dosing within a cycle; see Section 5.2.3). For nonclinical events requiring skipping a dose(s), must consult with and obtain approval by sponsor medical monitor. At least 7 days must elapse between administrations of LV.

Postdose

- Vital signs (within 30 minutes of ending each infusion, and during infusion as clinically indicated; see Section 7.6.2)
- Blood samples for PK assessment (C1 and C4 only; see Section 7.3 for time points)

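### No mandatory hold of ladiratuzumab vedotin (LV) in the visible protocol is tied to the combined potential Hy's Law laboratory pattern: at a normal baseline, ALT/AST >3 to 5 x ULN with bilirubin >2 to 3 x ULN clears every liver criterion for dosing

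*Protocol*

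**What the plan says.** **Dosing criteria (Protocol 5.2.3.1).** On Day 1 of each cycle, AST, ALT and total bilirubin must each be at Grade 2 or lower, alongside a neutrophil criterion. For Parts B and C a neutrophil minimum also applies "prior to LV administration on Day 8 and Day 15 (if receiving q1wk dosing) of each cycle"; no liver value is named for those days. The consequence of failing is: "If the above criteria are not met on the day of dosing, hold the LV dose until the criteria are met".

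**Liver panels on dosing days.** The Part B Day 8 list (6.3.3.3) includes "Serum chemistry panel and liver function tests (see Section 7.6.3; results to be submitted to iRIS), Cycles 1 and 2 only". The same line appears for Part B Day 15, Part C Day 8 (all arms) and Part C Day 15 (Arm 3).

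**Dose modification (Tables 10, 12 and 14).** For Grade 1 and Grade 2 non-hematologic toxicity other than neuropathy and hyperglycemia, the instruction is "Continue at same dose level". At Grade 3, LV is withheld until the toxicity is no worse than "Grade 2 or has returned to baseline, then resume treatment at same dose level". Grade 4 also leads to a withhold.

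**Withholding text.** Section 5.2.4.2 says that with "an AE or lab criteria that prevents dosing of LV (see Section 5.2.3.1), the LV dose for the week should be withheld". The matching sentence in 5.2.4.3 (Part C Arms 1 and 2) begins "In the event of an AE or lab criterion that prevents dosing of LV (see Section 7.6.1", so it points to the adverse event section instead of the dosing criteria.

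**Potential drug-induced liver injury (7.6.1.2).** A potential Hy's Law case has three parts: ALT and/or AST above 3 x ULN; total bilirubin above 2 x ULN without elevated alkaline phosphatase (ALP); and no other immediately apparent cause. Such a case is handled as a SUSAR. ALT or AST above 3 x ULN is to be retested within 48 to 72 hours and investigated. On dosing, the section only suggests that the site consider a hold meanwhile.

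**The concern.** The dosing criteria read the liver one analyte at a time, whereas the danger signal in 7.6.1.2 is a combination. A subject can be moderately abnormal on both analytes, satisfy each criterion separately, and still show the pattern that 7.6.1.2 treats as grave even when it occurs once.

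If so, a site that infuses LV on the day it finds the pattern and a site that holds are both compliant. Dosing during the work-up exposes the subject to further drug before the abnormality has been confirmed or explained. It also blurs the dechallenge information on which a causality judgement depends. The weekly and 2q3wk schedules sharpen the question, because their first scheduled post-dose liver panel, Cycle 1 Day 8, falls on a dosing day for which 5.2.3.1 sets no liver criterion.

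**Working it through.** There is no planned figure to reproduce. The check is an overlap of thresholds, followed by a search for any instruction that would compel a hold inside the overlap.

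**Inputs**
- Day 1 limit: AST, ALT and bilirubin each at Grade 2 or lower (5.2.3.1).
- Grade 2 at a normal baseline: AST/ALT >3.0 to 5.0 x ULN; bilirubin >1.5 to 3.0 x ULN (5.3.4.1, Table 15, footnote a, which follows CTCAE v5.0).
- Laboratory thresholds of a potential Hy's Law case: ALT/AST >3 x ULN and bilirubin >2 x ULN (7.6.1.2).

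**Overlap at a normal baseline**
- ALT/AST: above 3 and at most 5 gives (3, 5] x ULN.
- Bilirubin: above 2 and at most 3 gives (2, 3] x ULN.

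Examples, as ALT / bilirubin in multiples of ULN:

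| Values | Grades | Both Hy's Law thresholds met | Day 1 liver criteria |
|---|---|---|---|
| 3.1 / 2.1 | 2 / 2 | yes | pass |
| 4.0 / 2.5 | 2 / 2 | yes | pass |
| 5.0 / 3.0 | 2 / 2 | yes | pass |
| 5.1 / 2.5 | 3 / 2 | yes | fail |
| 4.0 / 3.1 | 2 / 3 | yes | fail |

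**Abnormal baseline.** Footnote a then grades relative to baseline. Entry allows ALT/AST up to 1.5 x ULN, or 3 x ULN with liver metastases (4.1), so the Grade 2 ceiling could reach 5 x 1.5 = 7.5 or 5 x 3 = 15 x ULN. The normal-baseline range is the conservative one.

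**Does any other visible text compel a hold inside the overlap?**
1. Tables 10, 12 and 14: graded by analyte, both values are Grade 2, so LV continues. After a Grade 3 value, LV restarts at Grade 2, which may still lie inside the pattern.
2. Section 5.2.4.2 refers back to 5.2.3.1, which the pattern passes.
3. Section 5.2.4.3 refers to 7.6.1, where the liver text leaves the hold to judgement.
4. Section 7.6.1.1 makes potential liver injury a serious event and may have the condition recorded instead of the laboratory value. The visible text does not fix the grade of such a condition, so a table withhold does not automatically follow.
5. Section 7.6.1.6 requires the sponsor to be told within 24 hours, but sets no dosing action.

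**Dosing days in Cycles 1 and 2 with a scheduled liver panel but no liver criterion in 5.2.3.1**
- q1wk: 2 days (8 and 15) x 2 cycles = 4 of 3 x 2 = 6 doses.
- 2q3wk: 1 day (8) x 2 cycles = 2 of 2 x 2 = 4 doses.
- q3wk: 0 of 2, because Days 8 and 15 are not dosing days.

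These counts describe 5.2.3.1 only. A Grade 3 or 4 liver toxicity found on those days is withheld under Table 12 or 14, so the gap on Days 8 and 15 is the Grade 2/Grade 2 combination. From Cycle 3, the latest scheduled result is 8 - 1 = 7 days old on Day 8 and 15 - 1 = 14 days old on Day 15.

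**Two liver definitions.** Section 7.6.1.2 uses >3 and >2 x ULN with no elevated ALP; 7.6.1.6 uses at least 3 and at least 2 x ULN with ALP below 2 x ULN. ALT 4, bilirubin 2.5 and ALP 1.5 x ULN is an event of clinical interest under 7.6.1.6. Its ALP is elevated, so it is not a potential case under 7.6.1.2. A hold rule needs one definition.

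**The case against.** The best reply is that the protocol does respond to this pattern and leaves only the dosing step to the investigator. It requires SUSAR handling, a prompt repeat test, medical assessment and follow-up to resolution. The sponsor's Drug Safety Department reviews serious events in real time (7.6), and benefit-risk is monitored continuously (9.3.9). Discretion has a rationale: the laboratory values alone do not make a potential Hy's Law case, because the third element is the absence of another evident cause, and liver metastases are allowed at entry. No liver term appears among the events in at least 20% of subjects, the most common Grade 3 or higher events, or the most common serious events listed for LV monotherapy (191 q3wk and 81 q1wk subjects in SGNLVA-001). ALT and AST increases reach 20% only with pembrolizumab.

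Much of this stands. A reader might infer that the Day 8 and Day 15 liver panels have no bearing on dosing. That is wrong, since Tables 12 and 14 apply on any day. A reader might also infer that no hold rule exists anywhere. The documents cannot show that: 7.6.1.2 and 7.6.1.6 refer to guidance in site binders, which is not visible here. Nor is Table 15, which withholds pembrolizumab for Grade 2 liver events regarded as immune-related, a rule that LV should be presumed to share.

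What does not stand is that discretion closes the gap. The protocol imposes fixed LV holds elsewhere, for Grade 2 neuropathy and for glucose above 250 mg/dL. Inside the overlap, its visible LV tables tell the site to continue.

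**Conclusion.** The point holds in a limited form. In the visible protocol, no mandatory LV hold is tied to the combined laboratory pattern. At a normal baseline the uncovered region is ALT/AST >3 to 5 x ULN with bilirubin >2 to 3 x ULN, on Day 1 and on Days 8 and 15. A same-day result can be followed by an infusion at 0 days, against 2 to 3 days to the repeat test.

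This rests on grading each analyte separately with the Table 15 cut-offs, and on the binders containing no hold rule. The documents give no rate for the pattern, and the number of cases is probably small. They do not support reading this as evidence that LV is causing liver injury, as proof that subjects will be re-dosed into harm, or as grounds for compulsory permanent discontinuation. It is a cheap improvement to a safety rule.

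**What to change.** Add to 5.2.3.1, with a footnote to Tables 10, 12 and 14 so that it overrides the Grade 2 and restart cells:

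> On any dosing day, if the most recent available results show ALT or AST >3 x ULN with total bilirubin >2 x ULN and no cholestasis, hold LV until the repeat tests and the Section 7.6.1.2 assessment are complete. Resume with medical monitor approval if another cause is documented and the usual dosing criteria are met. A persistent pattern with the same documented cause does not re-trigger the hold unless it worsens. If no other cause is found, the decision to resume or discontinue LV is made with the medical monitor.

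In 7.6.1.2, refer to this rule when both thresholds are met, and keep the discretionary wording for ALT/AST >3 x ULN alone. Use one ALP rule and one set of cut-offs in 7.6.1.2 and 7.6.1.6. No new pembrolizumab rule is needed. If the binder guidance already sets a hold, cite it in 5.2.3.1.

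**Cost.** Wording in three sections and three table footnotes; no new tests or visits. A few doses would be delayed, some in subjects later found to have another cause such as liver metastases. Under q1wk dosing a withheld dose may be skipped to the following week. Under 2q3wk, Day 8 may be withheld up to 4 days, so a 2 to 3 day retest can fit, but a longer assessment may lose the dose. From Cycle 3 the rule usually has no same-day result on Days 8 and 15.

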5.2.4. Dose Modifications

5.2.4.1. Part A (q3wk dosing)

Dose modification guidelines for LV q3wk treatment-associated toxicity are described in [Table 9](#). The maximum doses after modifications are:

- 200 mg for subjects reduced to 2.0 mg/kg
- 150 mg for subjects reduced to 1.5 mg/kg

Table 9: Q3wk LV dose levels

Dose Level	Dose	Maximum Dose
Starting dose	2.5 mg/kg	250 mg
-1	2.0 mg/kg	200 mg
-2	1.5 mg/kg	150 mg

[Table 10](#) describes dose modifications for LV treatment-associated toxicity.

Doses reduced for LV-related toxicity should not be re-escalated.

If a subject has a clinically significant, unresolved AE on Day 1 of C2 or beyond, the start of the cycle may be delayed for up to 14 days. Delays of >14 days must be approved by the medical monitor.

In the event a subject is unable to tolerate their dose level, additional treatment cycles (C2 or later) may be administered at a lower dose level upon approval by the medical monitor.

Table 10: Dose modifications for LV-associated toxicity (Part A; q3wk dosing)

Toxicity	Grade 1	Grade 2	Grade 3	Grade 4
Peripheral neuropathy ^a	Continue at same dose level	Withhold until toxicity resolves to \leq Grade 1; then resume treatment at the next lower dose level	Withhold until toxicity resolves to \leq Grade 1, then resume treatment at the next lower dose level	Discontinue treatment
Non-hematologic ^a (except peripheral neuropathy and hyperglycemia)	Continue at same dose level	Continue at same dose level	Withhold dose until toxicity is \leq Grade 2 or has returned to baseline, then resume treatment at same dose level ^b	Withhold dose until toxicity is \leq Grade 2 or has returned to baseline, then reduce dose to the next lower dose level and resume treatment, or discontinue at the discretion of the investigator ^{b,c}
Hematologic ^a	Continue at same dose level	Continue at same dose level	Withhold until toxicity resolves to \leq Grade 2 or baseline ^{d,e} . For neutropenia, strongly consider G-CSF support , then resume treatment at the same dose level. Prophylactic G-CSF support should be strongly considered for subsequent cycles. (See Appendix G)	Withhold until toxicity resolves to \leq Grade 2 or baseline ^{d,e} . For neutropenia, strongly consider G-CSF support , then resume treatment at the same dose level. Prophylactic G-CSF support is required for all subsequent cycles. If Grade 4 neutropenia recurs despite G-CSF support, consider dose reduction to dose level -1 or discontinuation. (Appendix G)
Febrile neutropenia ^a			G-CSF support is required for treatment of febrile neutropenia. Withhold until febrile neutropenia resolves and neutrophil count returns to \leq Grade 2 or baseline then resume treatment at the same dose level. Prophylactic G-CSF is required for all subsequent cycles. If febrile neutropenia recurs despite G-CSF factor support, consider dose reduction to dose level -1 or discontinuation.	
Hyperglycemia	Hold for blood glucose >250 mg/dL or >13.9 mmol/L. Resume treatment once elevated blood glucose has improved to ≤ 250 mg/dL or ≤ 13.9 mmol/L and subject is clinically and metabolically stable (see Section 5.6 for detail).			

Note: For subjects weighing ≥ 100 kg, dosing will be based on 100 kg for these individuals with a maximum calculated dose of 250 mg per infusion when dosed at 2.5 mg/kg.

a Only 2 dose reductions are allowed. Additional toxicities should be managed with dose delays

b Subjects who develop Grade 3 or 4 electrolyte laboratory abnormalities may continue study treatment without interruption if a management plan consistent with institutional practice and regular monitoring are put in place

c Treatment should be discontinued for subjects who experience Grade 4 infusion-related reactions

d Support with blood product transfusions allowed per institutional standard of care

e Subjects who develop Grade 3 or 4 lymphopenia may continue study treatment without interruption

